10.3.4. Exploration of unmeasured confounding

As it may not be feasible to collect all potential variables associated with treatment choice or bleeding outcomes (such as individual lifestyle choices) due to the nature of the study and maximizing data quality for the study when working with an existing registry (see Section 10.5), it is possible that residual confounding exists as a result of unobserved variables not included in the PS, which could influence the direction and/or magnitude of results observed. Therefore, the E-value, as reported by VanderWeele and Ding, will be used to explore this further (VanderWeele 2017).

The E-value is the minimum strength of association, on the risk ratio scale, that an unmeasured confounder would need to have with both the treatment and outcome, conditional on the measured covariates, to explain away a treatment–outcome association. The E-value focuses on the magnitude of the confounder associations that could produce confounding bias equal to the observed treatment–outcome association.

E-value calculations are straightforward. For an observed risk ratio of RR:

$$\text{E-value} = \text{RR} + \sqrt{\text{RR} \times (\text{RR} - 1)}$$

The formula applies to a risk ratio greater than 1; for a risk ratio less than 1, one first takes the inverse of the observed risk ratio and then applies the formula.

The interpretation of the E-value along with a qualitative assessment, including clinical input from HCPs in Germany, will be incorporated into the interpretation of results.

10.3.4.1. Baseline comparison of groups for propensity score development

Participant characteristics will be presented for all baseline variables described in Table 3 and Table 4, along with tests for difference using appropriate statistical testing; Welch's t-test for continuous variables, and the Chi-square test for categorical variables.

Standardized mean difference (SMD) will be calculated for continuous and categorical variables. SMD represents the most commonly used statistic to examine the balance of covariate distribution between groups, with a value greater than 0.1 indicating imbalance between groups (Zhang 2019).

After propensity score methods have been applied, tabulations will be repeated with p-values and SMDs re-calculated to investigate any meaningful differences remaining after PS-adjustment, both in the characteristics included in the propensity scoring, and also those not included. Although all baseline characteristics will be presented for completeness, the balance of the variables included within the PS models will be the focus of interest due to the importance assigned to these characteristics.

In accordance with guidance that model-evaluation tools of the logistic regression are secondary to the balancing of participant characteristics (McMurry 2015; Rubin 2004), sensitivity analyses will also be performed with the omission of highly correlated variables.

10.3.5. Application of the Propensity Score

Multiple PS adjustment methodologies have been considered for the primary analysis, with the specific method decided based on observations in the initial data cut for the interim analysis at 18 months after study initiation based on the hierarchy of methods outlined in the SAP. Considering the intended sample sizes as well as the primary question of interest (eg, the benefit of Roctavian vs SoC), weighting methodologies will be preferred and *a priori* the primary analyses will utilize inverse probability of treatment weighting (IPTW). IPTW will utilize all available data compared to matching approaches and estimate the Average Treatment Effect (ATE). Sensitivity analyses will be performed using alternative methods. Propensity score matching (PSM) is planned to be utilized as the main sensitivity method *a priori*. As the primary analysis plans to utilize IPTW and the *a priori* sensitivity analysis is planned to be PSM, these methods have been discussed below in Section 10.3.5.1.

Inverse probability treatment weighting IPTW will be implemented to create a baseline reference of propensity score weights for comparison. Using this approach, each participant is assigned a weight representing the inverse probability of being assigned to their respective group. Thus, IPTW aims at giving more importance (ie, more “weight”) to those participants that have unexpected propensity score values. For the treated group (Roctavian Cohort), the weight, W , assigned in the IPTW method for each individual, i , based on propensity score, P_i , is:

$$W_i = \frac{1}{P_i}$$

For the control group (SoC Cohort), participants receive weights of:

$$W_i = \frac{1}{(1 - P_i)}$$

As the characteristics of the population that will be treated with Roctavian are unknown at the time of this protocol being drafted, it is possible that large differences in characteristics between the Roctavian and SoC Cohort will exist. If this is the case, some participants may have extreme PS weights and, though representing a small portion of the observed population, have a disproportionate influence on the analysis. This outsized influence of individuals with extreme weights may increase variance and confidence intervals of the average treatment effect estimate ([Chesnaye 2022](#)). The SAP outlines approaches that will be taken in the case of extreme weights (eg, trimming) and criteria when these approaches will be implemented.

10.3.5.1. Propensity score matching

Propensity score matching will be considered *a priori* for a sensitivity analysis and initially be performed using the procedure of 1:4 matching. The PSM method matches each participant in the Roctavian Cohort with four participants in the SoC Cohort exhibiting the nearest PS (this is also known colloquially as ‘greedy’ matching) without replacement. For

the PSM, a caliper width of 0.2 times the standard deviation of the propensity score will be used ([Austin 2011](#)) and ‘random’ order. If the 1:4 matching ratio is not achievable at the specified caliper with >90% of the Roctavian Cohort matched to four SoC participants, a 1:3 matching ratio will be attempted, followed by a 1:2 matching ratio and then a 1:1 matching ratio as needed based on the requirement to match >90% to the relevant ratio. If the 1:1 matching ratio is not achievable, results for PSM will not be reported.

10.3.6. Primary Objective

10.3.6.1. Objective: To compare the annualized bleeding rate for treated bleeds.

Annual bleeding rates for treated bleeding events (see [Table 6](#)) will be compared between the Roctavian Cohort and SoC Cohort after PS adjustment. *A priori* the PS adjustment is planned to be implemented via IPTW. All participants with the variables recorded to derive the PS will be included in the analysis. Participants with no bleeds reported but data entered into the DHR will have an ABR of zero (ie, data is not considered missing).

ABRs will be compared over the full follow-up time for each participant in the study, as well as during annual increments during the follow-up. For analyses of annual increments, only those participants who have full follow-up for the time will be included in analyses. For example, analyses comparing ABRs during the first year will only include participants with ≥ 1 year of follow-up after the index date or analyses comparing ABRs through 2 years of follow-up will only include participants with ≥ 2 year of follow-up after the index date.

Sample sizes are expected to be reduced in analyses of annual increments for interim analyses as data collection will be ongoing, and potentially reduced for final analyses due to censoring (see below).

ABRs will be calculated for each participant as the number of bleeds divided by the time between the start of follow-up and censoring event for the analysis, annualized to the number in 1 year. The mean of the individual participant ABRs for each cohort will be calculated and compared. The primary comparison of ABRs will be based on the absolute difference in the mean treated ABR between the Roctavian Cohort and SoC Cohort utilizing a two-sample t-test (two-sided).

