7.1.2. Ongoing Data Collection

Data is expected to be entered into the DHR consistent with existing practices at study sites and applicable local regulations. It is expected that data will be entered into the DHR on an annual basis at a minimum, though may be more frequent if entered after each visit to an HTC.

In order to maximize the interpretability of interim analyses, study sites will be asked to enter data specifically for these analyses, which may fall outside of annual reporting at a site (see [Section 10.4](#)). Trained site monitors will provide support to participating sites to minimize the incidence of missing data through routine on-site monitoring visits and remote routine monitoring visits, tailored to each site depending on the number of participants enrolled and data entry compliance into the DHR (see [Section 11.8](#)).

Furthermore, prior to each planned interim analysis reporting period, site monitors will perform on-site monitoring visits to ensure that all available data has been recorded into the DHR for enrolled participants only.

Data on ongoing events (see [Table 6](#), [Table 7](#), and [Table 8](#)) will be entered into the DHR after the index date for a period of 3 years for each participant (based on the index date for that participant).

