8.2. Lost to Follow-Up

It is not anticipated that participants will be lost to follow-up due to the routine clinical management of PwSHA, as well as data being collected consistent with ongoing disease management practices. However, a participant may be considered lost to follow-up if he repeatedly fails to attend visits at the study site or does not respond to attempts at contact made by the study site. A participant will be deemed lost to follow-up at the discretion of the participant's treating physician, as participants are expected to be seen consistent with routine clinical management. As PwSHA are expected to be seen at an HTC at least annually

(and likely every 6 months), a participant may be considered lost to follow-up if he has not been seen, or no data has been reported into the DHR (whichever is later) for 18 months. Before a participant is deemed lost to follow-up, the treating physician or designee should make every effort to regain contact with the participant.

For the purposes of analyses, a participant's follow-up will be censored at the end date of the most recent data entry period into the DHR. At the time of final data cut, any participant without data entered into the DHR over the full follow-up period of this AbD (index date + 3 years) will be considered lost to follow-up and similarly censored. In reporting participants lost to follow-up, participants deemed lost to follow-up at the discretion of the investigator will be reported separate from those considered lost to follow-up at the time of the final data cut.

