10.2. Populations for Analysis

All participants who consent to participate in this study and fulfill the inclusion/exclusion criteria (see Section 5.2) will be described, though the population analyzed may differ from the overall population if data is missing for a variable required for a specific analysis. Minimal missing data is expected as most fields required for the analysis in the DHR are mandatory and data monitoring (see Section 7.1.2) will ensure timely and completeness of data entry for all relevant fields.

For specific analyses, the population included will be required to have data collected for the outcome of interest required for the analysis (eg, participants with a missing Haemo-QoL-A score at baseline would be excluded from an analysis of change from baseline in Haemo-QoL-A or a comparison of participants achieving the minimal clinically important differences [MCID] for the Haemo-QoL-A). *A priori* requirements for analyses are detailed further in the SAP, as for certain analyses the absence of an event (eg, bleed events) are not considered missing. The population not included in an analysis due to missing data will be described if ≥ 10 participants in each study cohort are excluded. Additional requirements/exclusions for specific analyses based on observations in the data (notably after the initial data cut for the first interim analysis) will be documented in the SAP and described in reports.

The cohorts for comparison in this study include:

- **Roctavian Cohort:** PwSHA without a history of or current inhibitors administered Roctavian during the study recruitment period.
- **SoC Cohort:** PwSHA without a history of or current inhibitors treated with exogenous FVIII replacement therapies or emicizumab and not administered Roctavian during the study recruitment period.

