The proportion of participants utilizing any hemostatic treatments during follow-up will be described but will not be compared as 100% of the SoC Cohort will utilize hemostatic treatments. The relative risk of participants utilizing any hemostatic treatments specifically for bleeds or short-term prophylaxis will be compared consistent with the proportion of participants with zero bleeding events. Also consistent with the analysis of the proportion of participants with zero bleeding, only those participants with follow-up for the full time over which the proportion is calculated will be included in analyses.

The total FVIII per kg administered during follow-up will be compared between the cohorts. Total FVIII per kg for any reason will be compared based on the absolute difference in the mean total FVIII per kg between the Roctavian Cohort and SoC Cohort utilizing a two-sample t-test (two-sided). Similar to the analyses of the proportion of participants with zero bleeding, only those participants with follow-up for the full time over which the proportion is calculated will be included in analyses.

Annualized infusion rates (AIRs) will also be compared between the cohorts. AIRs will be calculated for each participant as the number of infusions or injections divided by the time between the start of follow-up and censoring event for the analysis, annualized to the number of infusions/injections in 1 year. The mean of the individual participant AIRs for each cohort will be calculated and compared. The comparison of AIRs will be based on the absolute difference in the mean AIR between the Roctavian Cohort and SoC Cohort utilizing a two-sample t-test (two-sided).

10.3.7.4. Objective: To compare joint health, quality of life, and pain.

Descriptive statistics will be used to summarize the absolute and change from baseline at the time of assessment for the HJHS. A repeated measurement analysis model will be utilized to describe the overall trend in the HJHS over time. The mean change from baseline to final assessment approximately 3 years after index date will be compared between the Roctavian Cohort and SoC Cohort.

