7.9.4.3. Use of Hemostatic Medications

Population	Measurement Period	Analysis Notes
All participants For interim and analyses at fixed timepoints, only those with specified amounts of follow-up will be included	≥1 year of follow-up, ≥2 years of follow-up, ≥3 years of follow-up, all available follow-up	Participants with no treatment will be included as having a treatment value of 0

Cumulative hemostatic medication use will be compared between the Roctavian and the following SoC sub-Cohorts:

- FVIII treatment use (IU/kilogram [kg])
- Emicizumab treatment use (milligrams [mg]/kg)

The SoC Cohort will be stratified by participants using FVIII treatments and participants using emicizumab. They will separately be compared to the Roctavian Cohort. The amount of total (prophylactic and on-demand) treatments utilized per participant per kg (IU/kg or mg/kg; see Table 4) will be calculated across the follow-up period and calculated between the Roctavian, SoC, FVIII, and emicizumab Cohorts with the same follow-up measurement approach as the primary ABR outcome (see Section 7.9.3). Each participant's average weight over the reporting period will be used when calculating IU/kg. Prophylaxis and on-demand use will be described as available.

The proportion of participants utilizing any hemostatic treatments during follow-up will be described but will not be compared, as 100% of the SoC, FVIII, and emicizumab Cohorts will utilize hemostatic treatments. The use of FVIII for different reasons recorded in the DHR will also be described for each Cohort. For the emicizumab Cohort, the number of injections and regimen utilized (if possible, will be described). The proportion of participants utilizing any hemostatic treatments specifically for bleeds or short-term prophylaxis will be compared regarding the absolute difference in the proportion of participants utilizing a Chi-square test. Similar to the analyses of the proportion of participants with zero bleeding, only those participants with follow-up for the full time over which the proportion is calculated will be included in analyses.

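### Unreported intervals before a participant's latest registry entry count as bleed-free time in the primary annualised bleeding rate

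*Protocol*

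**What the plan says.** Three protocol rules act together.

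- **Zero rule.** Section 10.3.6.1: "Participants with no bleeds reported but data entered into the DHR will have an ABR of zero (ie, data is not considered missing". Section 10.2 makes the general point that "the absence of an event (eg, bleed events) are not considered missing". The table at the head of SAP Section 7.9.3 repeats the zero rule without the condition that data have been entered.
- **Denominator.** Section 10.3.6.1 defines each participant's rate as "the number of bleeds divided by the time between the start of follow-up and censoring event for the analysis", annualised.
- **End of follow-up.** Section 8.2: "follow-up will be censored at the end date of the most recent data entry period into the DHR". Its next sentence treats anyone without data over the full three years at the final cut as lost to follow-up and censors them in the same way.

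On reporting frequency, Section 7.1.2 says: "It is expected that data will be entered into the DHR on an annual basis at a minimum". Section 8.2 lets the physician consider a participant lost when he has not been seen or "no data has been reported into the DHR (whichever is later) for 18 months". Table 6 identifies a treated bleed from a therapy-usage record and names no field that positively confirms a bleed-free period.

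**The concern.** In an event registry, a zero is an observation only if someone reported on the period. Here the zero depends on data being in the registry, without saying that they must cover the interval, and exposure runs on to the latest entry. A missed annual report followed by a later one is therefore analysed as a year without bleeding.

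This affects the primary rate, the secondary bleeding rates built the same way, and the proportions with zero bleeds, where an uncovered year can pass as a bleed-free one. The study feeds a benefit assessment, so error in either direction matters. Time after the latest entry is censored and is not part of the problem.

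**Working it through.** **1. Trace one participant through the rules.** He reports year 1, misses year 2 and reports year 3. The most recent entry period ends at 36 months, so Section 8.2 censors him there. The final-cut sentence does not help, because it uses the same censoring point, which lies after the gap. Section 10.3.6.1 divides by 36 months. Year 2 contributes no recorded bleeds, and Section 10.2 says their absence is not missing. SAP Section 7.9.5.1 does not impute outcomes.

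**2. Size for that participant.** Scored rate = true rate × (36 − gap months)/36. This assumes he bleeds at the same rate during the gap. With a true rate of 3 (the SoC design value in Section 10.1):

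| Interior gap | Scored rate | Error |
|---|---|---|
| 6 months | 3 × 30/36 = 2.5 | −17% |
| 12 months | 3 × 24/36 = 2.0 | −33% |
| 18 months | 3 × 18/36 = 1.5 | −50% |

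**3. Reproduce the design.** Inputs from Section 10.1 and SAP Section 7.6: rates 3 (SoC) and 0.85 (Roctavian), θ = 0.2, φ = 1.5, exposure 1 year, R0 = 0.5, one-sided α = 0.025, power 80%.

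- V1 = 1/3 + 1/(0.2 × 0.85) + 1.2 × 1.5/0.2 = 15.22
- V0 = (1 + 0.5 × 0.2)²/[0.5 × 0.2 × (3 + 0.2 × 0.85)] + 9 = 12.82
- N1 = (1.960 × √12.82 + 0.842 × √15.22)²/[log 0.5 − log(0.85/3)]² = 328.8

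This gives 329 + 66 = 395, against the stated 330 + 67 = 397. Power at 330/67 is 80.6%. The design is reproduced to within two participants.

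**4. Cohort-level effect.** If a share g of counted time is uncovered, and gaps are unrelated to bleeding, the observed mean rate is the true mean × (1 − g). The documents give no value for g, so these are assumed values. The difference is the primary measure in Section 10.3.6.1.

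| Uncovered share | SoC rate | Roctavian rate | Difference | Ratio |
|---|---|---|---|---|
| none | 3.00 | 0.85 | 2.15 | 0.283 |
| 10% in both | 2.70 | 0.765 | 1.94 | 0.283 |
| 20% in both | 2.40 | 0.68 | 1.72 | 0.283 |
| 10% in SoC only | 2.70 | 0.85 | 1.85 | 0.315 |
| 20% in SoC only | 2.40 | 0.85 | 1.55 | 0.354 |
| 20% in Roctavian only | 3.00 | 0.68 | 2.32 | 0.227 |

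Equal gaps cancel in the ratio but not in the difference. For the ratio test against 0.5 in SAP Section 7.9.3, SoC-only gaps of 10% and 20% lower the power from 80.6% to 63% and 40%, with dispersion and sample size as designed.

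**5. Compare with the SAP's other derivations.** SAP Table 3 builds the baseline rate from reporting-period start and end dates and annualises by the amount of history available. In SAP Table 5 the zero-bleed rows also name those two fields. The treated-bleed rate row does not.

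**The case against.** The strongest reply is that Section 10.3.6.1 simply separates a reported period without bleeds from no report, which is normal for event data. Section 7 has study data entered on annual forms timed from the index date, and Section 7.1 makes the listed fields mandatory. Section 7.1.2 adds on-site visits before each interim analysis. Section 11.8 plans full source verification of primary endpoint fields and anticipates at least two on-site visits per site per year. SAP Section 7.9.5.1 will report missingness for outcome variables and compare it between cohorts. The 18-month clause only guides a physician's judgement.

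Much of this stands as a reason to expect few gaps. It does not change what the analysis does with those that occur. Section 11.8 itself accepts that missing data cannot be wholly avoided. Section 10.5 says the registry will be treated as the source for verification, which sits badly with checking registry entries against medical records. And if an absent bleed is by definition not missing, a missingness report need not reveal the gap.

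Three stronger inferences are not supported:

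- **That the bias favours Roctavian.** Nothing in the documents shows this. SAP Section 7.10 expects that Roctavian participants may be seen more often, which would point, if anything, to more gaps under SoC and a bias against Roctavian.
- **That a lone questionnaire or joint score earns a rate of zero.** This sits badly with the annual forms and mandatory fields.
- **That the plan disproves its own rule.** Section 10.3.7.3 notes that "100% of the SoC Cohort will utilize hemostatic treatments", and SAP Section 7.9.4.3 that "Participants with no treatment will be included as having a treatment value of 0". The first explains why one proportion is not compared. The second covers FVIII and emicizumab amounts, for which true zeros are expected. Neither says that a blank SoC period is scored as zero treatment.

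**Conclusion.** The point holds as a defect in the analysis rule: an unreported interval before the latest entry enters the primary endpoint as bleed-free time. Each cohort's rate falls by its own uncovered share. The direction of the bias in the comparison depends on which cohort has more gaps, and the size cannot be known from the documents. The 33% figure applies to one participant with a 12-month gap. The fall from 2.15 to 1.94 assumes 10% uncovered time in both cohorts and bleeding at the usual rate during gaps.

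A reader might infer that the rule would reverse the study's conclusion at the 0.5 margin. That needs a true ratio close to 0.5 as well as an assumed gap share. At the design ratio of 0.283, even 20% SoC-only gaps leave the ratio at 0.354. The supported claim is bias of unknown size and sign, with possible loss of power, and it should be corrected.

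**What to change.** In Section 10.3.6.1, define at-risk time as the days covered by submitted registry reporting periods, built from the start and end dates of those periods. Then:

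- score zero bleeds only for covered periods;
- leave uncovered days out of the rate denominator and the model offset;
- do not count uncovered days towards the full follow-up required for zero-bleed proportions;
- raise a data query for any SoC reporting period with no therapy record;
- report uncovered days by cohort, and keep the present rule as a sensitivity analysis.

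Carry this to Sections 10.3.7.1 and 10.3.7.2, SAP Sections 7.9.3, 7.9.4.1 and 7.9.4.2, and the treated-bleed row of SAP Table 5.

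The cost is wording and programming, plus some follow-up lost where reports are missing, which is little if gaps are as rare as the protocol expects. The start and end fields are already named for other variables but must be added to the treated-bleed derivation. SAP Tables 3 and 5 list no indicator that a therapy or bleeding section was completed, so coverage has to rest on submitted periods unless the registry can supply one.
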